7.1 Experimental design and study plan

This randomized, open-label, single dose, four-treatment, four period crossover design (4x4) trial with a 14-day wash-out period along 4 study stages will investigate the bioequivalence (primary endpoints are AUC_{0-t} , $AUC_{0-\infty}$ or C_{max} for Metformin and Gliclazide) of a Metformin/Gliclazide fixed combination tablet (1000 mg /30 mg MR) compared with the co-administration of the individual tablets (Metformin 1000 mg and Gliclazide 30 mg MR) and the drug-drug interaction between the Metformin/Gliclazide fixed combination and the administration of each single tablet, administered in fasted condition in 40 healthy volunteers. Secondly, safety and tolerability will be also investigated in every case.

The subjects will be randomized to one of the 4 treatment sequences (see table below). Ten subjects will be randomized to each treatment sequence with a minimum proportion of 30% for each sex in each treatment sequence.

Sequence	Period 1	Wash-out period	Period 2	Wash-out period	Period 3	Wash-out period	Period 4
1	Fixed combination		Metformin + Gliclazide		Metformin		Gliclazide
2	Metformin + Gliclazide		Gliclazide		Fixed combination		Metformin
3	Metformin		Fixed combination		Gliclazide		Metformin + Gliclazide
4	Gliclazide		Metformin		Metformin + Gliclazide		Fixed combination

7.2 Rationale for Study Design

As per international clinical guidelines about Type 2 Diabetes management (Diabetes Care, 2014), Metformin, if there are no contraindications and if this is tolerated, is the drug of choice for Type 2 Diabetes. In the event Metformin monotherapy at the maximum tolerated dose does not maintain hemoglobin A1c under 7% as target for more than 3 months, then it will be necessary to add a second oral agent from another pharmacological family, such as sulphonylureas, thiazolidine, DPP4i or GLP-1-RA. Gliclazide is a second generation sulphonylurea which offers a complementary mechanism of action for Metformin.

On the other hand, there is wide experience about Metformin's and Gliclazide's association and it is particularly recommended for some clinical guidelines (Treatment Algorithm for Type 2 Diabetes, 2014) when Metformin's monotherapy is not enough to achieve treatment objectives. Therefore, a fixed dose combination has been developed as second line therapy, in cases when Metformin's monotherapy has not shown satisfactory benefit/risk.

Fixed dose combination for Metformin and Gliclazide is a generic for the existent concomitant administration of these two active ingredients which use is already generalized. Fixed dose combination has the potential advantage of making easier the therapy by reducing the number of individual dosage units to be taken by the patient. This simplifies therapy and may improve patient's compliance (Diabetes Care, 2014; Treatment Algorithm for Type 2 Diabetes, 2014.)

In case of combinations which contain the active ingredients (as proposed in this study) and with a replacement indication (i.e., use in adequately controlled patients with individual products administered simultaneously, at the same dosage level than in the combination, but in different tablets), bioequivalence should be proven between free formulations combination and marketing formulation (fixed combination) (EMA, 2009).

On the other hand, international guidelines recommend that in case of new fixed combinations, it is necessary to assess the degree which drugs affect mutually the appropriate pharmacokinetic pattern (drug - drug interaction) (EMA, 2009).

Likewise, in Mexico, the committee to assess the marketing approval for new molecules (New Molecules' Committee) in case of new fixed dose combinations requests evidence about the lack of interaction between compounds making up the combination (drug - drug interaction) (COFEPRIS, 2013).

Clinical trial herein proposed is designed to achieve objectives stated by international guidelines as Mexico's Health Authorities in the field of bioequivalence and interactions. Although both objectives could be studied in two separate clinical trials (bioequivalence crossover design 2 x 2 and a cross interaction design 3 x 3), it is deemed more efficient to combine them in a single study. This reduces the number of subjects exposed as well as the minimization of time and costs. Therefore, the purpose of this clinical trial is mainly demonstrating bioequivalence and the drug-drug interaction of the new fixed dose combination for Metformin 1000 mg plus Gliclazide 30 mg MR compared to the concomitant dosage of individual tablets of Metformin 1000 mg XR and Gliclazide 30 mg MR. As secondary objective clinical safety and tolerability for all treatments used will be assessed.

7.3 Study population screening

Only those subjects who meet all inclusion criteria and none of the exclusion criteria will be recruited as study subjects. Before performing any study specific assessment which is not part of the subject's routine health care, the Principal Investigator will make sure that the subject has provided his/her written consent form according to the procedure described in section 10.2, Subject's information and informed consent form.

- ✚ Recruitment by invitation by means of an open announcement.
- ✚ Inclusion of 40 subjects in study as per protocol's criteria.
- ✚ Female and male subjects (at least 30% of each gender per treatment sequence).

7.3.1 Inclusion criteria:

For study inclusion, all of the following criteria must be fulfilled:

1. Subject has given written informed consent before any study-related activities are carried out
2. Ethnicity origin: Mexicans (e.g., Caucasian, Indigenous people and mestizos [mixed race])
3. Gender: male and female (at least 30% of each gender)
4. Age between 18 and 55 years old, inclusive.
5. Weight between 55 and 95 kg.

6. Body mass index between 18.5 and 27 kg/m².
7. Not smoking more than 5 cigarettes or 1 cigar or 1 pipe per day (or non smokers).
8. Good physical and mental health, determined on the basis of the medical history and a physical examination.
9. All results from blood chemistry, hematology, and urinalysis should be within normal ranges or without clinically significant deviations as per Principal Investigator's judgment.
 - ✓ Hematology complete blood count [CBC]: hematocrit and hemoglobin must be above the lower limit; upper limit may range up to 15 %. Remaining results, including white blood cells may range \pm 15 %, if subject is asymptomatic.
 - ✓ Liver Function Test (LFT), including: direct and indirect bilirubin, glutamic oxaloacetic transaminase (aspartate aminotransferase) and SGPT (ALT), total proteins, albumin, globulin and albumin/globulin ratio. Total bilirubin from 0.00 to 1.6 mg/dL, direct bilirubin from 0.0 to 0.4 mg/dL and indirect bilirubin from 0.0 to 1.2 mg/dL. They may range up to 15 % the enzyme's upper limit. Lower limit has no restriction for subjects' inclusion.
 - ✓ Blood chemistry (BC) including at least: glucose, urea, creatinine and uric acid. Asymptomatic subjects without family history of Diabetes or renal failure may be included with values ranging \pm 15 %.
 - ✓ Lipids panel including total cholesterol and triglycerides. Asymptomatic subjects without family history of dyslipidemia may be included with values ranging \pm 15 %. Lower limit does not have restriction for subject's inclusion.
 - ✓ Urinalysis (UA): asymptomatic subjects without history of renal failure may be included with values of urinary density ranging \pm 1 %. pH should be within 5 and 7. They can be included with albumin trace.
10. Electrocardiogram recording (12-lead) without signs of clinically relevant pathology in particular QTc (Bazett) <450 ms.
11. Vital signs (blood pressure and pulse) in supine position within normal ranges or showing no clinically relevant deviation as judged by the medical Investigator.
 - ✓ Heart rate between 50 and 100 beats per minute.
 - ✓ Respiratory rate between 12 and 20 per minute.
 - ✓ Systolic blood pressure between 80 and 129 mmHg.
 - ✓ Diastolic blood pressure between 50 and 89 mmHg.
 - ✓ Temperature between 36.0 and 37.0 °C.

12. All women of child bearing potential who are not pregnant or breastfeeding and who are using a highly effective contraceptive method (defined as those, alone or combined, which failure rate is low, i.e., less than 1 % a year, when used continuously and correctly) for at least one month before and following dosing. Barrier methods and intrauterine device are considered standard contraceptive methods. Hormonal methods will not be included. Post-menopausal women can be included (i.e., those with at least 12 consecutive months of amenorrhea following their last menstruation period) or surgically sterile/hysterectomy for at least 6 months before their participation in the study.
13. All women of childbearing potential must have negative tests for pregnancy (qualitative and quantitative) at screening, and at day -1 for each treatment period and at EOT as described in section 9.4.3
14. Negative result for oral alcohol screening at the beginning of each visit (day -1 for treatment period) and illegal drugs abuse (opioids, barbiturates, cocaine and its metabolites, amphetamines, metamphetamines, morphine, cannabinoids, benzodiazepines and tricyclic antidepressants), throughout the screening period and start of each one of the visits (day -1 for each treatment period).
15. Serology tests negative for human immunodeficiency virus (HIV1 and HIV2 antibodies), hepatitis A (HAV), hepatitis B (HBV), hepatitis C (HCV) and VDRL test screening. Valid for 3 months.

7.3.2 Exclusion criteria:

1. Participation in a clinical trial within 90 days prior to first drug administration.
2. Subjects who have donated more than 500 mL of blood or who have lost significantly (more than 450 mL) blood within 90 days prior to first drug of administration.
3. Any surgical or medical condition, including findings in the medical history or in the pre-study assessments, or any other significant disease, that in the opinion of the investigator, constitutes a risk or a contraindication for the participation of the subject in the study or that could interfere with the study objectives, conduct or evaluation.
4. History of surgery of the gastrointestinal tract which could influence the gastrointestinal absorption and/or motility according to the Investigator's opinion.
5. Allergy: ascertained or presumptive hypersensitivity to the active drug substance and/or formulations' ingredients; history of anaphylaxis to drugs or allergic reactions in general, which the Investigator considers may affect the outcome of the trial.
6. Receipt of any prescription or non-prescription medication within 2 weeks before the first study drug administration, including multivitamins and herbal products (e.g. St John's Wort), including ASA, and hormonal contraceptives in females.
7. Renal failure or renal dysfunction (creatinine clearance <80 mL/min) as assessed by using the estimated measure with the Cockcroft-Gault formula.

8. Known lack of subject compliance or inability to communicate or cooperate with the Investigator (e.g. language problem, poor mental status).
9. Considerable diet deviations from normal nutritional patterns.
10. Consumption of large quantities of methylxanthine-containing beverages (more than 600 mg caffeine / day: one cup (240 mL) of coffee contains approx. 100 mg of caffeine, one cup of tea ~ 30 mg and one glass of cola ~ 20 mg caffeine).
11. Consumption of grapefruit, orange, cranberry or juices of these fruits, 14 days prior to drug administration and during the study.
12. Legal incapacity or limited legal capacity.
13. Subjects kept in detention.

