1. Subject has given written informed consent before any study-related activities are carried out
2. Ethnic origin: Mexicans (e.g. Caucasians, Indigenous peoples and Mestizos)
3. Age between 18 and 55 years old, inclusive.
4. Female and male subjects (at least 30% of each gender).
5. Weight between 55 and 95 kg.
6. Body mass index between 18.5 and 27 kg/m².
7. Not smoking more than 5 cigarettes or 1 cigar or 1 pipe per day (or non smokers).
8. Good physical and mental health status, determined on the basis of the medical history and physical examination.
9. Vital signs (blood pressure and pulse) in supine position within the normal range or showing no clinically relevant deviation as judged by the Investigator.
10. Electrocardiogram recording (12-lead) without signs of clinically relevant pathology in particular QTc (Bazett) <450 ms.
11. All values for biochemistry and hematology tests of blood and urine within the normal range or showing no clinically relevant deviation as judged by the Investigator.
12. All women of childbearing potential (WOCBP) are not nursing, are not pregnant, and are using highly effective methods of birth control (defined as those, alone or in combination, that result in a low failure rate (i.e., less than 1 percent per year) when used consistently and correctly) for a period of at least one month before and after dosing. Standard birth control methods are considered to be: barrier methods and intra-uterine devices. Female volunteers may also be enrolled if they are postmenopausal (i.e. at least 12 consecutive months of amenorrhea after the last menstrual period) or surgically sterilized/ hysterectomized at least 6 months prior to study participation.
13. All women of childbearing potential must have negative tests for pregnancy (qualitative and quantitative) at screening, and at day -1 for each treatment period and at EOT as described in section 9.4.3.
14. Negative screen for alcohol and drugs of abuse (opiate class, barbiturates, cocaine and metabolites, amphetamines, cannabinoids, benzodiazepines and tricyclic antidepressants) at Screening and on each admission.
15. Negative screen for HBs antigens, HCV antibodies, HAV antibodies and HIV 1 and 2 antibodies.

Exclusion criteria:

Subjects are not eligible for this study if they fulfill one or more of the following exclusion criteria:

1. Participation in a clinical trial within 90 days prior to first drug administration.

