7.3.3 Criteria for Randomization

Eligible subjects will be rechecked at the time of admission to the study center (Day -1).

Results of the procedures performed on Day -1 as detailed Section 9.1.1, must be available prior to randomization. All inclusion and exclusion criteria will undergo a final verification before randomization.

7.3.4 Criteria for Subject Withdrawal from trial:

Subjects can be withdrawn from the study, as per the Principal Investigator's judgment, for the following reasons:

In case continuous participation in the trial is detrimental for subject's health, as per Investigator's judgment.

1. Hypertension signs and symptoms which require pharmacological treatment.
2. Syncope or shock.
3. Severe adverse reaction.
4. Serious Adverse Event.
5. Concurrent diseases or concomitant treatments not allowed by the protocol.
6. Lack of discipline.
7. Lack of compliance with the diet.
8. Lost of two samples within absorption period or near to the C_{max} .
9. If vomit occurs within therapeutic dosing interval, research subject should be withdrawn from the study and removed from the statistical analysis.

10. If any of the participant subject, during wash-out period, takes alcoholic beverages, smokes tobacco, has xanthenes containing beverages or food (coffee, tea, cacao, chocolate, mate, coke drinks, etc.) grapefruit, grapes or citrus, or grilled food (charcoal) within 24 h prior to the recruitment in the admission phase, or using any drug known by affecting the study.
11. Subjects with positive results to the drugs screening such as: amphetamines, benzodiazepines, cocaine, metamphetamines, morphine and tetrahydrocannabinoids.
12. Positive pregnancy test (qualitative or quantitative) following the study drug dosing.
13. All cases where the Principal Investigator judges as lack of compliance to the protocol or which may risk final results.

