7.4 Start-up Criteria for Study Treatment

- All women of childbearing potential should test negative for pregnancy qualitative and quantitative test at day -1 of each treatment period.
- All subjects must have negative result for oral alcohol screening at SCR and at the beginning of each visit (day -1 for treatment period) and drugs of abuse (opioids, barbiturates, cocaine and its metabolites, amphetamines, metamphetamines, morphine, cannabinoids, benzodiazepines and tricyclic antidepressants), throughout the screening period and start of each one of the visits (day -1 for each treatment period).

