7.5.1 Withdrawal from the study

A subject must be withdrawn from the study for any event which might risk subject's safety. In the event pregnancy tests during subjects' admission are positive, their participation will be stopped immediately (for further procedure in case of pregnancy see section 8.5.2).

A subject should be withdrawn from the study in case of any of the following:

- Voluntary subject's withdrawal.
- Lost to follow-up.
- Participation in another investigational study.

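### Inclusion 9 appears to admit volunteers with glucose up to 15 % below the laboratory's lower limit before fasted dosing, mostly with gliclazide; a one-sentence floor is a cheap safety improvement

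*Protocol*

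**What the plan says.** Inclusion 9 in section 7.3.1 of the protocol opens with a general rule: laboratory results must be "within normal ranges or without clinically significant deviations as per Principal Investigator's judgment". Bullets for each panel follow.

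- **Haematology:** "hematocrit and hemoglobin must be above the lower limit". Only their upper limit is relaxed, by 15 %. The other haematology results may vary by ± 15 % if the subject is asymptomatic.
- **Liver function and lipids:** the bullets say expressly that the low side carries no restriction.
- **Blood chemistry, with glucose named first:** "Asymptomatic subjects without family history of Diabetes or renal failure may be included with values ranging" ± 15 %. There is no separate wording for the low side.

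The Summary's criterion 11 gives only the general rule, again leaving the decision to the investigator, and has no percentage: "All values for biochemistry and hematology tests of blood and urine within the normal range or showing no clinically relevant deviation".

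Section 9.4.1.7 makes hypoglycaemia an adverse event of special interest and describes it as glucose usually under 70 mg/dL. Section 9.1.3 requires a fast of at least 10 h before and 4 h after each dose. Section 4 warns that gliclazide can cause hypoglycaemia, particularly when meals are missed.

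**The concern.** For a sulphonylurea given to fasting healthy volunteers, the low side of glucose is the side that matters for safety. Item 9 sets limits by direction for several tests, but gives glucose the same tolerance upwards and downwards. It therefore permits entry with a glucose that the laboratory would report as low and that the protocol's own description could class as hypoglycaemic.

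What is at stake is an avoidable risk to volunteers who gain no therapeutic benefit from the drug. The bioequivalence and interaction conclusions are not at stake.

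**Working it through.** The plan states no figure to reproduce here, so the check is a comparison of texts plus simple arithmetic.

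**Inputs.** Tolerance ± 15 % (7.3.1, item 9). Hypoglycaemia level 70 mg/dL (9.4.1.7). Dinner at 21:00 with 45 minutes allowed, and first meal from 12:00 (9.1.3). Dose at 08:00 (9.2.1). Forty subjects and four treatments, three of them with gliclazide (7.1). The laboratory's lower limit for glucose is not in the documents and is assumed over a range.

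**Step 1: lowest glucose admitted.** Reading the 15 % as a margin beyond the laboratory limits, floor = 0.85 × lower limit.

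| Assumed lower limit (mg/dL) | Floor now (mg/dL) | Floor after the fix (mg/dL) |
|---|---|---|
| 65 | 55.25 | 65 |
| 70 | 59.5 | 70 |
| 74 | 62.9 | 74 |
| 80 | 68.0 | 80 |

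**Step 2: when the floor falls under 70.** Solving 0.85 × limit = 70 gives 70 / 0.85 = 82.35. For any lower limit below about 82.4 mg/dL, the tolerance admits values under 70 mg/dL.

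**Step 3: the fast.** From the end of dinner (21:00 to 21:45) to the 08:00 dose is 10.25 to 11 h. Adding 4 h to the first meal gives 14.25 to 15 h in all.

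**Step 4: doses concerned.** Gliclazide doses are 40 × 3 = 120 of 40 × 4 = 160 planned. This is a ceiling on the doses concerned, not a count of doses at risk.

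**Step 5: do other provisions set an entry value for glucose?**

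- The lead sentence of item 9 and exclusion 3 (a finding that, "in the opinion of the investigator, constitutes a risk or a contraindication for the participation of the subject in the study") rely on judgment and give no number.
- Section 7.3.3 says "All inclusion and exclusion criteria will undergo a final verification before randomization". That check re-applies the same criteria, including the ± 15 %.
- Section 9.4.4 gives numeric limits on blood pressure and heart rate for a subject to continue, but none on glucose.
- Finger-sticks are scheduled before the dose and at 2, 4, 8, 12 and 24 h (9.1.2), with no entry value attached.
- Section 8.12 gives every subject 10 mL of 20 to 30 % glucose solution after the dose. One such amount is 10 mL × 20–30 % = 2–3 g. The section then speaks of two occasions, which implies about 4–6 g. This acts after dosing and does not affect entry.

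None of these sets a glucose value for entry. The only number bearing on a low screening glucose is the permissive one.

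**The case against.** **Judgment already applies.** The bullet permits inclusion and does not oblige it. The lead sentence and exclusion 3 both let the investigator refuse a worrying glucose, and section 7.5.1 adds that "A subject must be withdrawn from the study for any event which might risk subject's safety". This stands, and it is why the gain is modest. It does not explain why the one number offered points the permissive way.

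**The window is short and watched.** Subjects are confined until 48 h after the dose. They have finger-sticks before the dose and at 2 and 4 h, receive glucose solution and eat from 4 h. Section 3.2.2 has gliclazide rising progressively to hour 6 and level from 6 to 12 h, so much of the exposure comes after feeding starts. This also stands.

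**The haemoglobin contrast may have its own reason.** PK sampling alone takes about 880 mL of blood (9.5.1), which could explain the strict rule for red-cell measures. That is fair: the contrast shows that item 9 can set a limit in one direction, not that glucose was overlooked.

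**A screening value is not a pre-dose value.** Screening may be up to 30 days before the first dose, and section 9.1.1 does not say that the blood is taken fasting. A floor at entry is only a partial guide to glucose on four later mornings.

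**Stronger readings that the documents do not support.**

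- A reader might infer that glucose has no lower bar at all. The ± 15 % is itself a bar, and where the protocol means no restriction on the low side, as for liver tests and lipids, it says so.
- A reader might see a contradiction with the Summary. Criterion 11 there is the same lead rule in short form.
- A reader might go on to require a glucose hold rule before every dose in section 7.4, which now covers only pregnancy, alcohol and drug tests. That does not follow from this point. The protocol has fixed 14-day intervals and no provision for rescheduling a held dose. A subject who misses a period would fall out of the PK Analysis Set (9.9.3), using up part of the margin of 40 − 32 = 8.

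**Conclusion.** The point holds as a cheap improvement with a modest safety gain. Inclusion 9 states a rule under which a volunteer may enter with glucose up to 15 % below the laboratory's lower limit. For any limit below about 82.4 mg/dL, this includes values under the protocol's own 70 mg/dL description of hypoglycaemia.

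The conclusion rests on two assumptions: that the 15 % is measured from the laboratory limits, and that the laboratory's lower limit lies below about 82.4 mg/dL. The documents confirm neither. They also do not show how many subjects would be affected.

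**What to change.** In the blood chemistry bullet of section 7.3.1, item 9, add one sentence: glucose must not be below the laboratory's lower limit. Keep the rest of the bullet. The rule then also applies at the final verification before randomization (7.3.3), which in Period 1 follows the Day 1 finger-stick in the 9.2.1 schedule.

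The cost is a small, unknown number of extra screening failures. These occur before randomization and use none of the 40 places. If the change counts as substantial, both committees must approve it (11.5).

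Two limits remain. If the laboratory's lower limit were 65 mg/dL, values from 65 to 70 would still be admitted, because they are normal for that laboratory. And an entry floor does not guarantee the glucose level on later dosing mornings.
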